## C. Approach

**C1. Design and Procedures:** Consented participants will complete screening measures to determine eligibility. Eligible adult smokers will be randomly assigned in a 1:2:2 between-subjects design to either not receive an e-cigarette (control group, n=20) or receive one of two e-cigarette types: a customizable tank, or pods (n=40/each). Participants will sample their assigned e-cigarette, complete questionnaires, and then complete the choice task (described below). Participants will be provided with an e-cigarette device and e-liquid to sample over a three-week period (Figure 1). Across the study, participants will complete daily electronic diaries that assess their daily use of cigarettes and e-cigarettes. Participants will also complete weekly phone calls where they will complete assessments regarding tobacco use, craving, dependence, and product perceptions. At the end of the sampling period, participants will return to the lab to complete a series of questionnaires, complete the sampling and choice tasks again, and return the device.

**C2. Participants:** Daily cigarette smokers (n=100) will be recruited from the community. In/exclusion criteria are designed to enroll smokers who have limited experience with e-cigarettes. Inclusion criteria include adults who a) have been smoking at least five cigarettes daily for the past year (baseline CO > 8ppm), b) rate their interest in using e-cigarettes as >5 on a 0-10 scale, c) willing to use an e-cigarette as part of the trial, d) have a smartphone that can receive text messages and has access to the internet or have an e-mail account they check daily (necessary for daily diary completion) and e) be at least 21 years of age. Exclusion criteria include a) purchasing an e-cigarette within the last six months, b) weekly use of e-cigarettes over the last six months, c) any e-cigarette use in the past 30 days, d) use of tobacco products other than cigarettes on ten or more days in the past 30 days, e) current use of cessation medications, f) pregnant, trying to become pregnant, or breastfeeding, g) recent history of cardiovascular distress in the last three months, h) history of a seizure disorder, or i) household member currently enrolled. We will stratify group assignment based on age (21-30 vs. 31+) and motivation to quit (0-6 vs 7-10) to prevent these variables from being confounded with group.

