## C6. Statistical Analysis, Power, and Predicted Outcomes

**C6a. Statistical Analysis:** We focus on changes in reinforcement value of cigarettes because the public health impact of e-cigarettes will be driven by changes in the use of cigarettes, rather than any direct effects of e-cigarettes. Our primary outcome is the percentage of choices for each participant to smoke the conventional cigarette during the choice task at Week 3 (ranging from 0 to 100%). A one-way ANOVA model will be used to compare the e-cigarette groups, while excluding the control group, to examine the effect of e-cigarette type. If there is no significant difference between e-cigarette types, e-cigarette participants will be combined and compared to the control group via a t-test to examine the effect of e-cigarette sampling. Other outcomes will be analyzed using general linear mixed models (GLMMs) controlling for baseline values and repeated measurements per participant will be used to examine group, time, and group by time interactions. Our secondary aim focuses on the average number of cigarettes smoked per day during Week 3 while also examining average e-cigarette puffing episodes, expired carbon monoxide. These outcomes will be examined in a similar manner via GLMMs. We will also conduct exploratory analyses to determine whether the effect of e-cigarette type or e-cigarette sampling depended on individual characteristics such as age, gender, race, and motivation to quit. Given the innovative and exploratory nature of this trial, there are no existing datasets that directly apply for the purposes of conducting a power calculation. However, a sample size of 30 per e-cigarette group will provide 80% power to detect moderate between-group differences in a one-way ANOVA comparing the primary outcome with a two-sided alpha=0.05.

**C7c. Predicted Outcomes:** We hypothesize that the pod e-cigarette will result in further reductions in choices to smoke during the choice task and in cigarette smoking (Figure 2).

**C8. Future Directions:** The goal of the proposed application is to gain preliminary data on the impact of e-cigarette type. An R01 grant application will follow the proposed project and will include a longer sampling period, longer follow up period, a more thorough investigation of the health effects of e-cigarette types, and a full investigation of any critical moderators (e.g., age).

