#### 1.2 Study Procedures, Materials, and Potential Risks:

##### Study Procedures:

Participants will be screened over the phone to determine initial eligibility. Alternatively, participants may complete a redcap survey to determine initial eligibility. Participants will see a script that briefly explains the study. Once participants have been determined to be initially eligible, they will be invited to participate in the consent process. The consent process will take place via one of the following modalities: 1) Remote electronic consent (e-consent) via REDCap facilitated with a discussion over the phone, 2) Remote consent via doxy.me, or 3) in-person consent (in-person visit at start of Visit 1). We have built in the option for electronic consent to reduce the length of the first in-person visit and while still providing ample time for the consent process. Consented participants will be asked to attend an in-person screening session. We will provide transportation via a taxi cab company (Yellow Cab) for participants who are eligible, but do not have reliable transportation to in-person visits. We will pay the cab company directly, the participant will not need to contribute. Participants will be asked to provide a carbon monoxide sample to confirm smoking status, and women will provide a urine sample for pregnancy testing. Participants will then complete a series of interview-administered and participant-administered questionnaires that assess brief medical history, tobacco use history including prior and current e-cigarette and cigarette use, current use of smoking cessation products, and demographics. After all questionnaires have been completed, study staff will determine participant eligibility.

Participants who are eligible will then complete additional baseline questionnaires including measures of nicotine dependence. Participants will be randomized as described above and will have the opportunity to sample their usual brand cigarette and their assigned e-cigarette and e-liquid for the first time. After sampling each product, participants will complete additional questionnaires and complete the preference assessment where they choose between their cigarette and assigned e-cigarette. At the end of Visit 1, participants will receive a three-week supply of e-liquid to take home with their assigned e-cigarette, will be enrolled in the daily electronic diary system, and will be provided with instructions for completing diaries.

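### The primary pod-versus-tank ANOVA is valid but unadjusted, and may give up precision that smoking measures already collected before randomisation could supply

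*Combined protocol and SAP*

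**What the plan says.** C6a defines the outcome: "Our primary outcome is the percentage of choices for each participant to smoke the conventional cigarette during the choice task at Week 3". It then gives the test: "A one-way ANOVA model will be used to compare the e-cigarette groups, while excluding the control group, to examine the effect of e-cigarette type". No covariate appears in that model. For the remaining outcomes C6a says: "Other outcomes will be analyzed using general linear mixed models (GLMMs) controlling for baseline values".

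The Study Procedures in section 1.2 give the order of Visit 1. The CO sample and the tobacco use history, which includes current cigarette use, come first and feed the eligibility decision. Then: "Participants who are eligible will then complete additional baseline questionnaires including measures of nicotine dependence". Randomisation follows, then sampling of the usual cigarette and the assigned device, and only then the first choice task.

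On size, C1 randomises 40 to each device ("a customizable tank, or pods (n=40/each"). The power sentence in C6a uses a smaller figure: "a sample size of 30 per e-cigarette group will provide 80% power to detect moderate between-group differences in a one-way ANOVA", "with a two-sided alpha=0.05". It attaches no number to the word moderate, and C6a states that "there are no existing datasets that directly apply for the purposes of conducting a power calculation".

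**The concern.** How much and how dependently a person smokes at entry could plausibly influence how often that person picks their own cigarette in the laboratory. If so, an unadjusted ANOVA leaves that between-person variation in the error term and the confidence interval for the device difference is wider than it need be. The measures already exist, and assignment cannot affect them.

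Two features make precision matter here. The comparison is small. It also acts as a switch: under C6a, a non-significant device result leads to the two device groups being pooled and compared with control. A device difference missed for lack of precision therefore changes the analysis that follows.

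**Working it through.** **Inputs from the documents.** Two device groups; n = 40 per group (C1) or 30 per group (C6a power sentence); two-sided alpha 0.05; target power 80%.

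**Inputs assumed.** The share of variance in the Week 3 choice percentage explained by the covariates (R²): 0.10, 0.20 and 0.30, with 0 and 0.04 added to show the downside. A reference difference of 0.5 SD. The documents supply neither. They also give no SD, so results stay in SD units.

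**Step 1: the plan's own figure.** A two-group one-way ANOVA is a two-sided two-sample t-test. Power = P(|T| > t at 0.975), where T is noncentral t with 2n − 2 degrees of freedom and noncentrality d√(n/2).
- n = 30: power is 80% at d = 0.736 (noncentrality 0.736 × √15 = 2.85).
- n = 40: power is 80% at d = 0.634 (noncentrality 0.634 × √20 = 2.84).
- At d = 0.5, power is 47.8% with n = 30 and 59.8% with n = 40.

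The stated 80% can be neither confirmed nor refuted, because moderate has no value. With 30 per group it corresponds to about 0.74 SD.

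**Step 2: ANCOVA by formula.** Adjustment multiplies the residual SD by √(1 − R²), so d becomes d/√(1 − R²), and two covariates leave 2n − 4 degrees of freedom. For d = 0.5 the effective differences are 0.5/√0.90 = 0.527, 0.5/√0.80 = 0.559 and 0.5/√0.70 = 0.598. Power is then 52%, 57% and 62% with n = 30, and 64%, 69% and 75% with n = 40. The difference detectable with 80% power falls from 0.736 to about 0.70, 0.66 and 0.62 (n = 30), and from 0.634 to about 0.60, 0.57 and 0.53 (n = 40).

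**Step 3: ANCOVA by simulation.** The formula ignores chance imbalance of the covariates between groups, so it is slightly optimistic. Simulating a two-covariate ANCOVA at 0.5 SD, with imbalance allowed, gives the figures below. Ranges reflect differences between simulation runs.

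| Assumed R² | Power, n = 30 | Power, n = 40 |
|---|---|---|
| unadjusted | 48% | 60% |
| 0 | 46% | 58–59% |
| 0.04 | 48% | 61% |
| 0.10 | 50–51% | 63–64% |
| 0.20 | 55–56% | 68–69% |
| 0.30 | 61% | 74% |

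Break-even is near R² = 0.04, a multiple correlation of about 0.2.

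**Step 4: cost in degrees of freedom.** Two of 2 × 40 − 2 = 78 at 40 per group, or two of 2 × 30 − 2 = 58 at 30 per group.

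**Step 5: which measures qualify.** Cigarettes per day and dependence precede randomisation in the Study Procedures. The Visit 1 choice task does not: it follows both randomisation and first use of the assigned device, so it may already carry a device effect.

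**The case against.** The strongest objection is that the premise is not in the documents. No correlation between entry smoking and the choice percentage is reported, and even its direction can be argued. C5b offers three options (own cigarette, e-cigarette, abstaining), so a more dependent smoker might take more e-cigarette puffs instead of abstaining. All participants also smoke their own brand before sampling, to equalise time since the last cigarette, which may damp dependence-driven variation. A bounded score from 10 trials contains within-person noise that no baseline measure can explain. This stands, and it is why the gain must be stated as conditional.

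It can also be said that the plan's different treatment of the outcomes is understandable. The primary outcome has no pre-randomisation value of its own to adjust for, since the first choice task comes after assignment. That is fair, but other pre-randomisation measures are available.

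Third, the covariate list needs care. C5b and the Study Procedures refer to several dependence measures, so an unnamed score would leave a choice to the analyst. CO is also measured before randomisation, but each added covariate has a price. With three covariates that predict nothing, simulated power at the effect where the unadjusted test has 80% falls to about 78%. The stratification factors in C2, age and motivation to quit, are also absent from the primary model. Whether to include them is a separate question, best settled when the covariate list is fixed.

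A reader might infer more than the documents support:
- That the ANOVA is biased. It is not; it is a valid randomised comparison.
- That it certainly loses power. That depends on an R² nobody has reported.
- That adjustment is worth 11% to 43% more participants at no cost. Those figures are 1/(1 − R²) at R² of 0.10 and 0.30. They assume the correlation and ignore chance imbalance.
- That 30 per group is the planned enrolment. Thirty appears only in the power sentence; 40 per device group are randomised.

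**Conclusion.** The point holds as one of efficiency. The primary analysis omits pre-randomisation smoking measures that the trial already collects, and may be less precise as a result. At 0.5 SD and an assumed R² of 0.10 to 0.30, a two-covariate ANCOVA adds roughly 3 to 14 percentage points of power with either 40 or 30 per group. If the covariates predict nothing it costs about 1 to 1.5 points. The possible loss is small and the possible gain moderate, which favours pre-specifying the adjustment even though R² is unknown.

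The change does not rescue the power claim. Even at R² = 0.30 with 40 per group, power at 0.5 SD is about 74%, and the undefined word moderate remains a separate problem.

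**What to change.** In C6a, before outcome data are examined, make the primary analysis an ANCOVA of the Week 3 percentage of choices to smoke on device type (pod versus tank), with two covariates: pre-randomisation cigarettes per day and one pre-randomisation dependence score, identified by name. Report the unadjusted one-way ANOVA as a sensitivity analysis. State that the Visit 1 choice task is not used as a covariate, because it follows randomisation and sampling of the assigned device.

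The cost is a short amendment and two error degrees of freedom. It requires no new data, visits or participants.

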### **Concurrent Use of E-cigarettes & Smoking**

Per above, the most common effects from too much nicotine are nausea, headache, and disturbed sleep. The sampling period is three weeks in duration, and thus we do not expect sustained patterns of dual use. We will track adverse events at every study contact, and will have a toll-free number available for participants to call if they experience an adverse event (AE). All study contacts will remind participants of this number. Participants will be encouraged to contact study staff as soon as possible for serious events. If they wish, they may contact their local MD or give the study medical advisor permission to do so. We will withdraw participants who have a serious AE, become pregnant or begin breast-feeding. For other AEs, if the participant's physician or the participant wishes it, the participant will be withdrawn from the study.

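### The primary Week 3 ANOVA is completers-only by default and leaves the Visit 1 choice data unused, so it can bias the pod-versus-tank comparison if loss is related to liking the device and differs by arm.

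*Combined protocol and SAP*

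**What the plan says.** Section C6a defines the primary outcome as the "percentage of choices for each participant to smoke the conventional cigarette during the choice task at Week 3". For the test it says: "A one-way ANOVA model will be used to compare the e-cigarette groups", with the control group left out. No covariate or second occasion enters this model. The next method is kept for everything else: "Other outcomes will be analyzed using general linear mixed models (GLMMs) controlling for baseline values and repeated measurements per participant".

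The choice task is done twice. At Visit 1, after randomisation and after first sampling the assigned device, participants "complete the preference assessment where they choose between their cigarette and assigned e-cigarette" (section 1.2, Study Procedures). At the end of the three weeks they return to the lab and "complete the sampling and choice tasks again, and return the device" (section C1).

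Forty participants are randomised to each e-cigarette group (C1), but power is stated for "a sample size of 30 per e-cigarette group" (C6a). The difference is not explained. Section 2.2 adds a route out of the study: "We will withdraw participants who have a serious AE, become pregnant or begin breast-feeding". Withdrawal for other adverse events is at the wish of the participant or the participant's physician. The combined protocol and SAP states no analysis population, missing-data method, expected loss or missing-data sensitivity analysis.

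**The concern.** A one-way ANOVA on a single-visit outcome cannot use anyone who lacks that outcome. With no imputation planned, it compares those who came back. The Week 3 task is done in the lab, so a missed visit loses the primary outcome.

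Loss linked to the device is plausible on the protocol's own account. The Specific Aims describe tanks as harder to learn and pods as easy to use, and section A2a allows that complexity may reduce uptake. If people who prefer their cigarettes to the assigned device are less likely to return, and this happens more in one arm, the completers in the two arms are differently selected. The trial would then report a device difference that partly reflects who stayed.

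The Visit 1 task records each person's first preference between cigarette and device. It is done at the randomisation visit, so it should exist for nearly everyone randomised. It is the most direct information on selective loss, and the primary analysis does not use it.

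**Working it through.** **The plan's own figure.** With 30 per group and two-sided alpha 0.05, 80% power in a two-group ANOVA corresponds to a difference of 0.74 SD (noncentral t). The text says only that the difference is moderate, so the 80% cannot be reproduced without a number. At 0.5 SD, power would be 48%. The value 0.74 SD is used below only as a scale for the bias.

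**The 30 against 40.** 30/(1 − 0.25) = 40, so the gap is consistent with 25% loss. The text does not say so.

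**Inputs.** From the documents: 40 randomised per e-cigarette arm, Week 3 outcome, unadjusted two-group ANOVA, alpha 0.05. Assumed, because the documents give none: loss rates; correlation ρ of 0.5 to 0.7 between Visit 1 and Week 3 choices; standardised normal scores; and log-odds of loss rising by 1 per SD of Visit 1 smoking choices. The true device difference is set to zero.

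**Formula.** If loss depends on the Visit 1 score Y1, the completers' Week 3 mean in an arm is ρ × E[Y1 | stayed]. The bias is the difference between the two arms' values. Numerical integration gives E[Y1 | stayed] of −0.133 at 15% loss, −0.173 at 20%, −0.213 at 25%, −0.253 at 30% and −0.292 at 35%. It is 0 where loss is unrelated to Y1.

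| Loss in the two arms | Bias at ρ = 0.5 | Bias at ρ = 0.7 | Type I error (simulated) |
|---|---|---|---|
| 25%/25%, same pattern | 0 | 0 | 5% |
| 30%/20%, same pattern | 0.5 × (0.253 − 0.173) = 0.04 | 0.7 × 0.080 = 0.06 | 5% |
| 35%/15%, same pattern | 0.5 × (0.292 − 0.133) = 0.08 | 0.7 × 0.159 = 0.11 | 6 to 7% |
| 25%/25%, related to Y1 in one arm only | 0.5 × 0.213 = 0.11 | 0.7 × 0.213 = 0.15 | 7 to 9% |

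Finite simulations agree within sampling error; their lowest values are 0.03 in the second row and 0.10 in the fourth. The quoted ranges, 0.03 to 0.11 and 0.10 to 0.15 SD, include them.

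**Loss unrelated to choices.** At 35%/15% with no relation to the score, simulated bias is about 0 and type I error about 5%. Unequal loss alone is not enough.

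**Using both occasions.** When loss depends on Visit 1 choices, a likelihood estimate from both occasions has bias below 0.01 SD.

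**Where that fails.** If loss depends on the Week 3 score itself (35%/15%, same pattern, ρ 0.5 to 0.7), the ANOVA bias is about 0.16 SD and the two-occasion model still leaves 0.09 to 0.12 SD.

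**Direction.** If the arm losing more of those who prefer smoking is the tank arm, tank completers look better than they should, which works against the hypothesised pod advantage. If it is the pod arm, the bias favours pods. The documents do not settle which applies.

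**The case against.** The best defence is that loss may be small and not selective. Sampling lasts three weeks, the Week 3 visit pays $50, and there is a further $50 completion bonus (C4). Taxis are paid for those without reliable transport (section 1.2). Participants may use the device as much or as little as they like (Specific Aims), so disliking it is not in itself a reason to leave. A prior trial by the team had diary compliance above 90% (C5c), although that is not visit retention. The study also calls itself preliminary. These points stand. They lower the likely size of the bias, but they do not supply a missing-data method.

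Some stronger readings are not supported:

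- A reader might infer that the plan has a rule excluding non-attenders. It does not; completers-only is the default of the named model.
- A reader might infer that 25% attrition was planned. The power statement never links 30 per group to loss.
- A reader might expect much larger bias, 0.22 to 0.29 SD with type I error of 14 to 21%. That needs people who dislike the device to leave one arm while people who like it leave the other. The documents give no reason for this, and it does not fit the mechanism of dislikers leaving.
- A reader might see the withdrawal rule in section 2.2 as a main source of loss. Mandatory withdrawal covers only serious adverse events, pregnancy and breast-feeding, and the team reports no serious adverse events in its current e-cigarette studies. Continuing diaries or carbon monoxide measurement after withdrawal would not recover a lab-based choice task.

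**Conclusion.** The concern holds as a conditional one. The primary analysis is completers-only by default and leaves relevant, already collected data unused. It can bias the pod-versus-tank comparison. A reader might go further and conclude that the result will be biased, but that requires loss that is related to the outcome and differs by arm in rate or pattern, and the documents give no loss figures.

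Under the stated assumptions the effect runs from nil to modest. The largest value, 0.15 SD, is about a fifth of the 0.74 SD detectable with 30 per group (0.15/0.74 = 0.20). Neither the size in percentage points nor the direction can be given, because the documents state no SD, correlation or loss by arm. The mixed model is not a complete cure: it removes the bias only if data are missing at random given Visit 1. The change is still worth making, because it needs no new data and uses a class of model that the plan already applies to its other outcomes.

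**What to change.** Before analysis, amend C6a as follows:

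- Make the primary analysis a repeated-measures mixed model of percent choices to smoke at Visit 1 and Week 3, with group, occasion, group-by-occasion and an unstructured covariance. Report the Week 3 pod-versus-tank contrast as the primary result.
- Include all participants randomised to the two e-cigarette groups who have at least one choice task.
- Enter Visit 1 as an outcome, not a covariate. It follows randomisation and first use of the device, so adjusting for it could remove part of the device effect.
- Keep the one-way ANOVA as a sensitivity analysis.
- Add a missing-not-at-random sensitivity analysis, delta-adjusted separately by arm.
- Report loss by arm, and say whether the 30 in the power statement is an allowance for loss.

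The cost is SAP wording and slightly more analysis work. The price in assumptions is reliance on missing-at-random given Visit 1, which the delta-adjusted analysis is there to test. With complete data the Week 3 estimate equals the ANOVA difference, so little is given up if retention is high.

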In a between-subjects design, adult daily smokers (n=100) who are interested in trying e-cigarettes will be randomly assigned in 1:2:2 fashion to either a control group that receives no product (n=20), or to receive one of two types of e-cigarettes to sample over a three-week period: a) customizable tank, or b) pod, (n=40/group). The design is naturalistic in that participants receiving an e-cigarette will be told to use the e-cigarette as much or as little as they would like, allowing for assessment of self-determined uptake and reinforcement. Methods include both ecological assessments (electronic daily diaries) and experimental sessions (choice and purchase tasks). Biomarkers (expired carbon monoxide) will corroborate self-reported indices of use.

**Primary Specific Aim:** to assess the impact of e-cigarette product type (customizable tanks vs. pods) on product satisfaction ratings and relative reinforcement value (choices to smoke vs. use product in choice task, hypothetical purchase task). We hypothesize that pods will produce greater satisfaction ratings and relative reinforcement value than the customizable tanks.

**Secondary Aim:** to assess the impact of e-cigarette product type on tobacco use patterns including cigarette smoking (cigarettes per day, expired breath carbon monoxide) and e-cigarette uptake (e-cigarette puffing episodes). We hypothesize that pod style e-cigarettes will produce greater reductions in cigarette smoking compared to customizable tanks and greater uptake of e-cigarettes. Secondary analyses will compare the impact of e-cigarette sampling (control vs. all e-cigarette groups) on smoking during the sampling period.

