## C5. Measures

**C5a. Screening Assessments:** Preliminary eligibility will be determined on the phone before participants are either consented electronically or invited for an in-person visit to provide consent. Alternatively, participants may complete a Redcap survey to determine initial eligibility. Participants will see a script that briefly explains the study. Consented participants will attend an in-person visit where they complete screening questionnaires related to demographics, tobacco use history, and expired carbon monoxide.

**C5a. Measures of Subjective Effects:** Subjective effects will be assessed using a modified version of the Cigarette Evaluation Questionnaire (mCEQ), which assesses product satisfaction, psychological reward, craving reduction, enjoyment of sensations in the respiratory tract, and aversion. First, participants will sample their usual brand cigarette to standardize time since last cigarette. Participants will then sample their assigned e-cigarette and e-liquid. Immediately after sampling, participants will complete the mCEQ.

**C5b. Measures of Relative Reinforcement:** Relative reinforcement will be assessed using a lab-based choice task, a well-validated measure of reinforcement value. After participants sample their assigned product, they will complete choice task in which over a period of 30-minutes and 10 trials, participants choose between taking two puffs of the e-cigarette, two puffs of their usual (own) brand cigarette, or abstaining from both. Participants in the control group will choose between their usual brand cigarette and abstaining. In this case, the task will measure the impact of device type on changes in the relative reinforcement value of smoking compared to using the e-cigarette. The primary outcome is the number of choices to smoke. A secondary measure of reinforcement value will be purchase tasks—hypothetical tasks in which participants estimate the intensity with which they would use cigarettes and e-cigarettes at a variety of prices. The purchase tasks can be used to calculate several demand parameters, which are estimates of reinforcement value. Additional dependence measures will be included. [name] is utilizing these measures in recently completed and upcoming projects.

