**C5c. Measures of Tobacco Use and Biomarkers:** Daily cigarette use will be captured using an electronic daily diary (<2 min/day) in which participants report the number of e-cigarette puffing episodes per day and the number of cigarettes they smoked. This electronic daily diary was used in [name] recently completed trial with compliance > 90%. We will collect expired breath carbon monoxide at Randomization and the Week 3 visit, which provides an objective measure of recent smoke exposure but is unaffected by e-cigarette aerosol.

[figure not shown]
**C5d. Other Self-Report Questionnaires:** We will also use questionnaires to assess demographics, tobacco use history, expectancies, perceived health risks, and adverse events over time.

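### The conditional Week 3 choice-task test of pooled e-cigarette groups against control is read as a sampling effect, but only the e-cigarette groups are offered an e-cigarette in the task

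*Combined protocol and SAP*

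**What the plan says.** Section C6a takes as primary outcome the percentage of cigarette choices in the choice task at Week 3. Tank and pod are compared first, with controls left out. The control comparison is conditional: "If there is no significant difference between e-cigarette types", then "e-cigarette participants will be combined and compared to the control group via a t-test to examine the effect of e-cigarette sampling". No adjustment for the Visit 1 task is attached to this t-test. Baseline control is specified for the rest: "Other outcomes will be analyzed using general linear mixed models (GLMMs) controlling for baseline values".

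Section C5b defines the task. In the e-cigarette groups, "participants choose between taking two puffs of the e-cigarette, two puffs of their usual (own) brand cigarette, or abstaining from both". For controls: "Participants in the control group will choose between their usual brand cigarette and abstaining".

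Elsewhere, sampling mainly means the three-week take-home period (Specific Aims; C1). The Secondary Aim places the control contrast on use outside the laboratory: "Secondary analyses will compare the impact of e-cigarette sampling (control vs. all e-cigarette groups) on smoking during the sampling period".

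**The concern.** The outcome is the share of choices that go to the cigarette, and the menu differs between the two sides of this contrast. If some choices go to the e-cigarette simply because it is on offer that day, and would otherwise have gone to the cigarette, the e-cigarette groups score lower even if three weeks at home changed nothing. Under the plan's wording, that gap would be reported as evidence that sampling lowers the reinforcement value of smoking. The Week 3 level alone cannot separate the two explanations.

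The test is a likely reporting path. It runs whenever the device comparison is not significant, which is about 95% of the time if the devices are truly equal. C8 says the results are meant as preliminary data for a larger grant application.

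**Working it through.** **The plan's own figure.** C6a states 80% power with 30 per e-cigarette group for a moderate device difference. By the noncentral t distribution, 30 per group gives 80% power at 0.74 SD and 48% at 0.5 SD. Moderate is not given a number, so the 80% can be neither confirmed nor refuted. It concerns tank versus pod. No power, SD or expected difference is given for the control comparison.

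**Inputs from the documents.** Control n = 20 and e-cigarette n = 40 + 40 = 80 (C1); 10 choices per person (C5b); two-sided alpha 0.05 (C6a).

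**Assumptions, because the documents give no values.** There is no sampling effect and tank equals pod. The propensity p to smoke rather than abstain has mean 70% in every arm. The e-cigarette takes a mean share s of 10, 20 or 30% of choices. A factor f says how far those choices displace smoking: f = 1 if they draw proportionally from smoking and abstaining, 0.5 if smoking is displaced half as much, 0 if they replace only abstaining. The between-person SD in controls is about 26 or 34 points.

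**Gap.** Expected smoking is p in controls and p(1 − f·s) in the e-cigarette groups, so the gap is p·f·s.
- f = 1: 70 × 0.10, 0.20, 0.30 = 7, 14, 21 points.
- f = 0.5: 3.5, 7, 10.5 points.
- f = 0: 0 points.

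**Standard error.** SE = SD × √(1/20 + 1/80) = SD × √0.0625 = 0.25 × SD, that is 6.5 points at SD 26 and 8.5 at SD 34. A 14-point gap is then 14/6.5 = 2.2 or 14/8.5 = 1.6 standard errors.

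**Simulation.** Beta-binomial choices, pooled two-sample t-test, 40,000 trials per setting. Percentage of trials significant at shares of 10/20/30%:

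| Displacement of smoking | SD about 26 | SD about 34 |
|---|---|---|
| Full proportional (f = 1) | 18 / 54 / 87 | 12 / 35 / 66 |
| Half (f = 0.5) | 8 / 20 / 37 | 7 / 14 / 26 |
| None (f = 0) | 5 / 5 / 5 | 5 / 5 / 5 |

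Conditioning on a non-significant tank-pod test changes the full-displacement rates by 0.1 point or less.

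**Sensitivity, f = 1.** With mean propensity 60%, the rates are 14/42/75% (SD about 28) or 10/27/52% (SD about 36). With 15 versus 60 evaluable and mean 70%, they are 14/43/76% or 10/28/53%.

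**Cross-check.** A separately built simulation (control rate 70%, SD about 29) moved 10/20/30% of cigarette choices to the e-cigarette and gave 14/43/77% among trials with a non-significant tank-pod test. By noncentral t with SD 30, shifts of 5, 10 and 20 points give 10, 26 and 75%.

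**Would change from Visit 1 remove the problem?** Only if availability acts equally at both visits. Even with a constant share, unequal menus scale change differently. If propensity falls from 70% to 50% in every arm, controls fall 20 points, while the e-cigarette groups fall 20 × (1 − s) = 18, 16 or 14 points. They would appear to fall 2, 4 or 6 points less for no reason other than the menu.

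**The case against.** The strongest reply is that sampling is used loosely. The Secondary Aim glosses it in parentheses as control versus all e-cigarette groups, and C5b and section 1.2 also use the word for brief product use in the laboratory. On that reading the t-test simply compares assigned with not assigned, which is valid. The validity of that contrast stands. The label is not rescued, because an option offered only during the task is neither home sampling nor the brief use before the task.

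It can also be said that the consequence is limited. This is a conditional follow-up in a preliminary study, no stated hypothesis concerns controls on laboratory choices, and the aims already place the control contrast on smoking during the sampling period. That is fair; it keeps the remedy small.

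The figures are model-driven and run from 5 to 87%. That also stands: they show what could happen, not what to expect.

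Three stronger readings are tempting and not supported:
- *The test has an inflated type I error or is biased.* Under these assumptions assignment really does change choices in the task. The rates show how often the sampling label would mislead, not how often the randomized contrast is wrong.
- *The primary device comparison is compromised.* It excludes controls, and both device groups have the same menu.
- *The trial cannot assess sampling against control.* Cigarettes per day and expired carbon monoxide do not use the task.

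Section 1.1 of Protection of Human Subjects says that all participants receive an e-cigarette, which conflicts with the no-product control group in its own preceding sentence. The two need reconciling, but C5b is explicit on the control menu.

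**Conclusion.** The point holds as an error of interpretation in one conditional test. The Week 3 contrast with control estimates the effect of being assigned an e-cigarette, including its availability during the task, and cannot be read as the effect of sampling alone.

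That the menus differ is plain in the text. How much it matters depends on how far e-cigarette choices displace smoking, which the documents do not tell us: there is no problem if they replace only abstaining, and a substantial one if they displace smoking proportionally and take 20 to 30% of choices. The illustrations assume no sampling effect, equal propensity across arms and equal devices. It should be fixed, because the plan as written could report a sampling effect on reinforcement value where there is none, and the correction is one of wording.

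**What to change.** Add a limiting sentence to this test in C6a, for example:

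> Because controls have no e-cigarette option in the task, this comparison estimates the effect of being assigned an e-cigarette (availability during the task plus sampling) and will not be interpreted as the effect of sampling alone.

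Rest the control-versus-e-cigarette sampling conclusion on the planned baseline-adjusted cigarettes per day and expired carbon monoxide. For the latter, "We will collect expired breath carbon monoxide at Randomization and the Week 3 visit". Participants keep the device until the final visit, when they "complete the sampling and choice tasks again, and return the device", so these outcomes also reflect access to it. That is acceptable, because home access is the sampling intervention itself, whereas the task menu is set by the experimenter.

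Optionally, report change in choices from Visit 1 to Week 3 as supportive only. First confirm that controls complete the task at Visit 1: C1 implies it, but section 1.2 describes that session only as a choice between the cigarette and the assigned e-cigarette. State that the Visit 1 task follows randomization and first product use, and that change removes availability only if availability acts equally at both visits. A change in e-cigarette share after home use may itself be a sampling effect and should not be treated as spurious.

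Keep simulated rejection rates out of the SAP text.

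The cost is one sentence. No new data are needed and the primary ANOVA does not change. The downside is that the Week 3 choice-task level can no longer be claimed as evidence of a sampling effect against control.
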